4.8.4.4. Demographics and Baseline Characteristics

Demographic and baseline characteristics will be summarized for the evaluable registry population. Demographic and baseline characteristics will also be summarized for the registry population that is lost to follow-up and compared with the evaluable population to assess potential differences. These data will be reviewed for factors that could affect interpretations of comparisons with the external comparator cohort(s). Additional data including maternal age, previous pregnancy outcomes, pregnancy complications, concomitant medications, maternal concurrent medical conditions, SLE disease severity, maternal outcomes, and belimumab dosing will be summarized with simple descriptive statistics and data listings. Further details will be provided in the RAP.

4.8.5. Analyses for the unexposed group

Registry data will be used to produce data summaries for the primary endpoint of birth defects and descriptive analyses for all secondary endpoints (i.e. pregnancy and infant outcomes) for the unexposed group. The unexposed group will be treated as an aggregate exposure grouping, i.e. no analyses are planned by specific medication. Patients in the unexposed group may have had prior exposure to belimumab during the course of the SABLE protocol but were not exposed to belimumab within 4 months or during pregnancy; these patients may be analysed separately if sample size is sufficient.

While the number of unexposed pregnancies from the SABLE cohort is expected to be low, these pregnancies may be informative in exploring any potential signals. For example, if a unique anomaly is observed in both the exposed and unexposed cohorts, this finding may suggest an etiology other than belimumab exposure.

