4.4. Exposure Definition

For belimumab-exposed subjects: One complete or partial dose of commercially supplied belimumab, administered within the 4 months (i.e., a period of approximately 5 belimumab terminal half-lives) prior to and /or during pregnancy, will constitute exposure. Belimumab exposure will be further categorized by earliest trimester of exposure, as described in Section 4.8.2.2.

For belimumab "unexposed" subjects: Treatment with any immunosuppressants (azathioprine, methotrexate, cyclophosphamide, mycophenolate, biologics or others) as defined in the SABLE protocol as SLE treatment, excluding belimumab (Protocol HGS1006-C1124). There must be sufficient evidence to confirm that exposure to belimumab did not occur within 4 months prior to and / or during pregnancy for a woman to be classified within this group.

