4.8.1. Belimumab Exposed Participants

The summary statistics for continuous and categorical variables to be used will be specified in the Reporting and Analysis Plan (RAP) but may include means, standard deviations, medians, minimums, maximums, percentiles, and percentages. Frequencies and proportions of adverse pregnancy outcomes, birth defects, and serious and/or

clinically significant infections in infants will be calculated along with their 95% confidence intervals.

The registry data will be used to conduct risk estimation and comparative analyses for the primary endpoint of birth defects and descriptive analyses for all secondary endpoints (i.e. pregnancy and infant outcomes). The presence of a birth defect will be summarized for registry participants with SLE who have been exposed to commercially supplied belimumab within the four months prior to and/or during pregnancy. The birth defect prevalence will be calculated as the percentage of birth defects from the total number of live births [Parker, 2010]; this approach is commonly used in other drug exposure pregnancy registries [Covington, 2004; Tomson, 2004; Holmes, 2008]. Fetal losses occurring at or after 20 gestational weeks with reported birth defects will be included in the estimation for the risk for birth defects to increase sensitivity and to allow comparison of the registry birth defect rates with the CDC MACDP and EUROCAT surveillance systems. An analysis will also be conducted to include fetal losses with reported birth defects for birth defects occurring at less than 20 gestational weeks in the calculation of risk for birth defects.

Analyses will be stratified by subgroups of interest including: timing of exposure (i.e. prior to conception and after conception or during pregnancy as well as trimester or gestational week) and level of exposure (as indicated by dose and duration of belimumab dosing); gestational age at enrollment; maternal age; and region, such as North America and Europe. Additional details on subgroup analyses will be described in the RAP. Comparisons may be made to external cohorts, if appropriate.

Primary Endpoint:

• Birth defects

Secondary Endpoints:

Other pregnancy outcomes

- Spontaneous miscarriage
- Live birth (preterm birth and SGA)
- Stillbirth
- Elective termination

Infant outcomes through age 1 year

• Serious and/or clinically significant infections

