4.8.3.1. Population-Based Birth Defects Surveillance Programs

The Centers for Disease Control and Prevention (CDC) Metropolitan Atlanta Congenital Defects Program (MACDP) classification system will be used as the primary comparator data for defining and coding of birth defects for all registry sites. For the occurrence of birth defects, CDC MACDP data will be used for all sites as it is widely used as a comparator in pregnancy registries. The European Surveillance of Congenital Anomalies (EUROCAT) data will be used as a secondary comparison for European sites.

The primary objectives of CDC MACDP are to regularly and systematically monitor births of malformed infants to monitor changes in incidence or other unusual patterns and to develop a case registry for use in epidemiological studies. CDC MACDP actively searches for birth defects among the 50,000 annual births to residents of metropolitan Atlanta's 5 counties and abstracts medical records at all Atlanta obstetric hospitals, pediatric referral hospitals, genetics laboratories, and vital records [Correa-Villasenor, 2003]. CDC MACDP data have been used as a comparator cohort in examinations of birth defects for other pregnancy registries (acyclovir, sumatriptan, lamotrigine, and zidovudine) [Honein 1999]. The most recent CDC MACDP 5-year prevalence of 2.78% (6,945 cases with birth defects/249,999 live births) from 1999 to 2003 is deemed the most appropriate comparator birth defect data [Correa, 2007], due to lack of adequate birth defect data for the offspring of SLE mothers.

The total prevalence of birth defects overall in EUROCAT (including fetal deaths and pregnancy terminations) from 2004-2008 was 2.33% (http://www.eurocat-network.eu/). EUROCAT is a European network of population-based registries, including 43 registries in 20 countries, and it covers 29% of the European population. It started in 1979 and includes 1.5 million births per year in Europe. Its primary objectives are to provide essential epidemiological information on congenital anomalies and to act as an information and resource center to individuals and public health professionals.

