5. SAMPLE SIZE AND POWER/PRECISION CALCULATIONS

This registry will be descriptive and will seek to enroll approximately 500 traditional prospective pregnancies exposed to commercially supplied belimumab. Research indicates that approximately 83-95% of pregnancies enrolled in pregnancy exposure registries will result in a live birth [Covington, 2010] and approximately 20-25% will be lost to follow-up [Covington, 2007], resulting in an upper estimate of 380 live births and a lower estimate of 311 live births.

The study design will allow the birth defect prevalence in belimumab-exposed participants to be estimated with an exact 95% confidence interval (CI) of (1.32%, 5.09%) assuming 350 live births and an observed belimumab birth defect prevalence equivalent to the MACDP general population birth defect prevalence of 2.78%. It needs to be further determined which, if any, external data sources may provide appropriate comparison data for the different outcomes evaluated in this pregnancy registry.

The registry acknowledges the challenges of enrolling this number of exposed live births and will carefully monitor enrollment trends and outcomes. This will be an open registry with initiation of participant recruitment in participating countries from the time of launch. Recruitment will continue with periodic reports filed to global regulatory agencies until the accumulated sample size is deemed adequate.

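### No planned birth-defect rate separates co-exposure to other SLE drugs, and Section 4.8.5 rules out any analysis by medication in the unexposed group

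*Protocol*

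**What the plan says.** **Exposed group.** Section 4.8.4.2 estimates the difference between the registry's birth-defect rate and the MACDP and EUROCAT rates, with a 95% interval and no stated adjustment. Section 4.8.2.1 lists the exclusions from the primary population, and co-medication is not among them. Section 4.8.1 begins "Analyses will be stratified by subgroups of interest including: timing of exposure" and goes on to level of belimumab exposure, gestational age at enrollment, maternal age and region. In Section 4.8.4.4, concomitant medications belong to a list that ends "belimumab dosing will be summarized with simple descriptive statistics and data listings".

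**Unexposed group.** Section 4.4 describes it as "Treatment with any immunosuppressants (azathioprine, methotrexate, cyclophosphamide, mycophenolate, biologics or others) as defined in the SABLE protocol", leaving out belimumab. Section 4.8.5 then says "The unexposed group will be treated as an aggregate exposure grouping, i.e. no analyses are planned by specific medication". The same section gives the example of a unique anomaly found in both cohorts and comments that "this finding may suggest an etiology other than belimumab exposure".

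**Data held.** Sections 4.6, 4.6.2, 4.6.3.1 and 4.6.3.2 collect other SLE treatment with dates, from 4 months before conception and through pregnancy, as well as concomitant medications.

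**The concern.** Section 1.1 reports that belimumab was given in Phase 3 on top of baseline lupus medication, so co-exposure in the registry is plausible. If some of those drugs raise the risk of defects, the exposed rate carries their effect, and a general-population comparator does not share it. An excess over MACDP could then be read as a belimumab signal.

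The opposite error is also possible. If an unexposed woman's child has a defect caused by her own immunosuppressant, and a similar defect appears in the exposed group, the example in 4.8.5 points away from belimumab without asking what the unexposed woman took. Section 7.11 says that unexposed cases will be used in evaluating belimumab signals, so the example bears on planned work.

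**Working it through.** **Inputs from the protocol**
- Comparator (Section 4.8.3.1): "The most recent CDC MACDP 5-year prevalence of 2.78% (6,945 cases with birth defects/249,999 live births) from 1999 to 2003".
- Planned precision (Section 5): "exact 95% confidence interval (CI) of (1.32%, 5.09%) assuming 350 live births".
- Expected live births (Section 5): "resulting in an upper estimate of 380 live births and a lower estimate of 311 live births".

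**Inputs that are assumptions.** The protocol gives neither of these, and it does not call any of the named drugs teratogenic.
- s, the share of exposed live births co-exposed to a drug that causes defects: 2% to 20%.
- r, the defect risk in those births: 10% to 25%.

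**Step 1: reproduce the plan's figures.**
- 6,945 / 249,999 = 2.78%.
- 500 × 0.95 × 0.80 = 380, and 500 × 0.83 × 0.75 = 311.
- The Clopper-Pearson interval with 350 × 0.0278 = 9.73 cases is 1.325% to 5.093%, which agrees with the stated interval. The plan's arithmetic is sound.

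**Step 2: false-excess threshold at n = 350.** 16 cases give an exact lower limit of 2.64%. 17 cases (4.86%) give 2.85% to 7.66%. So 17 or more cases are needed before the lower limit exceeds 2.78%.

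**Step 3: expected rate if belimumab has no effect.** p = (1 − s) × 2.78% + s × r. For example, with s = 5% and r = 10%, p = 0.95 × 2.78% + 0.05 × 10% = 3.14%. The last column is the binomial chance of 17 or more cases in 350.

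| s | r | p | Chance lower limit > 2.78% |
|---|---|---|---|
| 0% | – | 2.78% | 2.0% |
| 2% | 10% | 2.92% | 3.0% |
| 5% | 10% | 3.14% | 5.3% |
| 5% | 20% | 3.64% | 14.3% |
| 10% | 20% | 4.50% | 40.9% |
| 10% | 25% | 5.00% | 58.4% |
| 20% | 25% | 7.22% | 97.1% |

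With 311 live births the threshold is 16 cases. The chances are then 1.5% with no co-exposure effect, 3.9% at 5%/10% and 49.0% at 10%/25%. With 380 the threshold is 18 cases and the chances are 2.1%, 5.8% and 62.7%.

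**Step 4: precision lost by restricting.** At an observed 2.78%, excluding 5% of 350 leaves 332 live births and an interval of 1.29% to 5.17%. Excluding 10% leaves 315 and 1.26% to 5.25%. The unrestricted interval is 1.32% to 5.09%.

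**Step 5: the unexposed side, by reasoning.** Section 4.4 makes other immunosuppressants part of the group's definition, while 4.8.5 rules out looking by drug. Yet 4.8.5 allows women with earlier belimumab exposure to be analysed separately if numbers suffice. Small numbers alone therefore do not explain why drug type gets no conditional split.

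**The case against.** A reader might infer that drug causes cannot be told apart at all. The protocol does not support that. Treatments and dates are logged, targeted follow-up seeks etiology and attribution (4.6.5), and the birth defect evaluator gives an opinion on temporal association with belimumab or other SLE treatment (7.10). Cases exposed to other SLE treatments enter signal review (7.11). With about 10 defects expected, such review is informative. What it does not do is change the prevalence or its difference from MACDP.

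Other points against the concern:
- **The analysis plan may cover the exposed side.** The list of strata in 4.8.1 is open, and 4.8.1 and 4.8.4.4 both defer detail to the Reporting and Analysis Plan, which is not at hand. This stands. It does not reach 4.8.5, where analysis by medication is expressly ruled out.
- **Confounding is acknowledged.** Section 6 names SLE medication as a possible confounder, and 4.8.4.2 plans comparisons with external SLE cohorts. Section 6 also says that confounder data may be lacking, especially in external cohorts. Restriction within the registry needs no external data.
- **The unexposed group is not a formal reference.** Section 4.8.3 rules out formal comparison and expects few participants, and the shared-anomaly remark is a hedged example. It should not be read as a rule for dismissing signals.
- **The primary estimate does not count every exposed pregnancy.** Section 4.8.2 limits it to pure prospective evaluable SLE cases. The 350 live births relate to 500 traditional prospective enrolments, so the primary set will be no larger than that total and probably smaller.
- **Group definition.** Section 4.1 requires only absence of belimumab exposure, without the immunosuppressant condition of 4.4. Some unexposed women may therefore have taken none of the named drugs. The two sections need reconciling; a yes/no flag works under either.

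**Conclusion.** The concern holds in limited form. No planned rate separates co-exposure to SLE drugs that may themselves cause defects. Section 4.8.5 fixes that choice for the unexposed group, and its shared-anomaly example leaves out the unexposed woman's own drugs. On the exposed side the gap is in the named analyses and may be closed in the analysis plan.

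The size is unknown. It rests on an assumed co-exposure share, an assumed defect risk, and the assumption that births without co-exposure carry the MACDP risk. If co-exposure is rare the effect is negligible: 3.0% against 2.0% at a 2% share and 10% risk. At 10% and 25% the chance of a false excess is 58%. The high figures come from the upper part of an assumed grid and are not a forecast. Severity is minor to moderate.

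**What to change.** 1. **Section 4.8.4.2:** add a sensitivity analysis of birth-defect prevalence, and its difference from MACDP, that leaves out pregnancies with recorded exposure to a prespecified list of known teratogens from 4 months before conception through the first trimester. Apply the exclusion to numerator and denominator alike. The list can sit in the Reporting and Analysis Plan, with the committee's teratology expert agreeing it before the data are analysed.
2. **Section 4.8.5:** replace the statement that there is no analysis by medication with a descriptive split of the unexposed group by the same yes/no flag, and a listing of unexposed defects by medication and exposure window.
3. **Section 4.8.5, example:** limit the reading of a shared anomaly as pointing away from belimumab to unexposed cases without such exposure.

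The cost is one derived flag, a few tables and a listing, all from data already collected. The sensitivity interval is slightly wider, as shown in Step 4, and cells in the unexposed split will be sparse, so that split should stay descriptive.

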4.8.6. Data Handling Conventions

Data will be managed with an electronic database, which is 21 CFR Part 11 compliant. The database will be backed up as part of the routine back-up process. The server will be backed up to tape daily as an incremental back-up (i.e., only files with changes since the last back-up will be backed up). A full back-up of the database will be performed weekly and stored securely off-site for 1 year. One full back-up per month will be stored off-site for 3 years; however, every 6 months back-ups will be responsible for retaining back-ups of the electronic database for the duration of the registry. On termination of all registry activities, the database and all electronic and paper files will be transferred to GSK for archiving.

5. SAMPLE SIZE AND POWER/PRECISION CALCULATIONS

This registry will be descriptive and will seek to enroll approximately 500 traditional prospective pregnancies exposed to commercially supplied belimumab. Research indicates that approximately 83-95% of pregnancies enrolled in pregnancy exposure registries will result in a live birth [Covington, 2010] and approximately 20-25% will be lost to follow-up [Covington, 2007], resulting in an upper estimate of 380 live births and a lower estimate of 311 live births.

The study design will allow the birth defect prevalence in belimumab-exposed participants to be estimated with an exact 95% confidence interval (CI) of (1.32%, 5.09%) assuming 350 live births and an observed belimumab birth defect prevalence equivalent to the MACDP general population birth defect prevalence of 2.78%. It needs to be further determined which, if any, external data sources may provide appropriate comparison data for the different outcomes evaluated in this pregnancy registry.

The registry acknowledges the challenges of enrolling this number of exposed live births and will carefully monitor enrollment trends and outcomes. This will be an open registry with initiation of participant recruitment in participating countries from the time of launch. Recruitment will continue with periodic reports filed to global regulatory agencies until the accumulated sample size is deemed adequate.

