In addition to challenges to maternal health, patients with lupus have poor obstetric outcomes compared with women without SLE, including a greater likelihood of fetal loss (approximately 3-fold increase) and a greater incidence of preterm deliveries [~40% vs. 10% among healthy women] [Clark, 2003; Clowse, 2005]. Recently a meta-analysis addressing this subject was reported [Smyth, 2010]. The proportion of pregnancies in women with SLE resulting in fetal death has been reported to be 15-20% in European studies [Cortes-Hernandez, 2002; Julkunen, 1993] and 15-25% in North American studies [Clowse, 2005; Andrade, 2008], with stillbirths accounting for 2-4% of these outcomes.

The presence of anti-phospholipid antibodies has been reported in 30-80% of patients with SLE [Mecacci, 2009], and associated with an increased risk of spontaneous miscarriage and poor maternal and/or fetal outcome [Cortes-Hernandez, 2002, Clark 2007]. In prospectively examined pregnancies, with anti-Ro and anti-La antibodies in the mother, the prevalence of congenital heart block (with mortality of approximately 20-30%) is between 1 and 5%, and rises to between 6 and 25% when another pregnancy was affected in the same mother [Jaeggi, 2010; Friedman, 2010]. Active SLE and associated comorbidities (proteinuria, anti-phospholipid syndrome, thrombocytopenia, and hypertension) have also been noted to be important predictors of fetal loss [Clowse, 2006; Cortes-Hernandez, 2002; Julkunen, 1993].

A cohort of SLE pregnancies from a single academic medical center in the US identified risk factors for fetal loss and preterm delivery. Among pregnant patients with high SLE disease activity (PGA score \geq 2), 42% had fetal loss during the first trimester compared to 14% among women with low activity (PGA<2). This pattern was observed during the second (32% vs.7%, respectively) and third trimesters (10% vs. <1%, respectively). The combination of high disease activity, with low complement and/or anti-ds DNA autoantibodies, during the second trimester increased the risk of fetal loss and preterm delivery pregnancy outcomes [Clowse, 2011].

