The primary safety population supporting approval of belimumab also included data from a Phase 2 study in 449 subjects with SLE (LBSL02). Treatment with belimumab plus standard of care was generally well tolerated, with rates of adverse events (AEs), severe AEs, serious AEs, AEs leading to discontinuation and serious/severe infections generally comparable to the rates observed in the placebo plus standard of care group. Mortality rates in the controlled clinical trials were low, although numerically higher in the belimumab groups: 0.4% and 0.8% in the placebo and belimumab groups, respectively. Causes of death were as expected in an SLE population with active disease receiving a wide range of standard therapies, such as steroids and immunosuppressants, and included infection, cardiovascular disease. Serious infections were observed in 5.2% and 6.0% of subjects receiving placebo and belimumab, respectively. The rate of malignancy (excluding non-melanoma skin cancer) was the same between the placebo and belimumab groups at 0.4%; as with other immunomodulating agents, the mechanism of action of belimumab might be expected to increase the risk for the development of malignancies. Hypersensitivity and infusion reactions were observed. Depressionrelated events, common in patients with SLE, were observed more frequently with belimumab than with placebo; it is unknown if belimumab treatment is associated with an increased risk for these events. The most commonly reported adverse reactions, occurring in \geq 5% of subjects in clinical trials were nausea, diarrhea, pyrexia, nasopharyngitis, bronchitis, insomnia, pain in extremity, depression, migraine, and pharyngitis.

Within the IV SLE studies, the number of pregnancies was small; 60 pregnancies (belimumab: 54; placebo: 6) with 50 known outcomes (belimumab: 44; placebo: 6) had been reported as of 31 December 2010. Subjects had been instructed to use contraception, had pregnancy tests before each belimumab or placebo infusion, and were withdrawn from treatment if the test was positive. Regardless of treatment, the incidence of fetal loss in the IV SLE studies was greater than the expected 15-25% fetal loss reported in the literature [Andrade, 2008; Clowse, 2005; Rahman, 1998; Yasmeen, 2001]. In subjects with known pregnancy outcomes (excluding elective terminations), fetal loss was reported for 13/34 pregnancies among subjects exposed to

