4.8.2.2. Analysis Parameters for Birth Defects

Most structural defects originate in the first trimester of pregnancy, the period of organogenesis. Therefore, the outcome data for pure prospective evaluable cases will be stratified by the earliest trimester of exposure to belimumab. For this registry, gestational weeks will be estimated from the most reliable EDD as reported by the HCP. If a CEDD is provided by the HCP, it will be used instead. The date of conception will be calculated as the most reliable EDD minus 38 weeks. If the EDD is not available or never estimated, the first day of the LMP may be used to estimate gestational age. The second trimester begins at week 14 after the date of conception or LMP, and the third trimester begins at week 28.

Only cases meeting the CDC MACDP criteria for a defect or with 2 or more conditional defects will be included in the primary study population. Single minor defects do not constitute a birth defect according to the CDC MACDP classification; therefore, they will be listed in the report, but not included in the primary study population.

The birth defect primary analysis will include pure prospective pregnancies and a sensitivity analysis with traditional prospective pregnancies is planned.

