Hypertension	Elevated blood pressure described as systolic blood pressure greater than 140 mm Hg or diastolic blood pressure greater than 90 mm Hg.
Last menstrual period (LMP)	The first day of the last menstrual period prior to conception.
Maternal death	The death of a woman while pregnant or within 42 days of termination of pregnancy, irrespective of the duration and site of the pregnancy, from any cause related to or aggravated by the pregnancy or its management but not from accidental or incidental causes.
Metropolitan Atlanta Congenital Defects Program (MACDP)	A program that monitors all major birth defects in 5 counties of the metropolitan Atlanta area (Clayton, Cobb, DeKalb, Fulton and Gwinnett) with approximately 50,000 annual births from a population of about 2.9 million. MACDP acts as the model for many state-based programs and as a resource for the development of uniform methods and approaches to birth defect surveillance.
Molar pregnancy	A conception that results in a gestational trophoblastic tumor.
Neonatal death	An infant who after live birth expired within the first 28 days of life.
Pre-eclampsia	A condition of pregnancy occurring after 20 weeks gestation characterized by hypertension, edema, and proteinuria
Preterm birth	An infant born at gestational age <37 weeks
Prenatal test	Diagnostic or screening evaluations that may give insight into the outcome of the pregnancy. Examples include ultrasound, amniocentesis, chorionic villus sampling, nuchal translucency testing, and maternal serum screening for aneuploidy or neural tube defects.

Term	Registry Definition
Proteinuria	The presence of excess protein in the urine. Proteinuria is typically assessed by urine dipstick (graded as trace or + (low) vs ++ to ++++ (medium- high)), or urine biochemistry on a spot urine (protein/creatinine ratio >30), or a 24 hour urine collection (300 mg protein/24 hours).
Pure prospective report	Pure prospective reports of pregnancy are a subset of traditional prospective reports and include those where (a) the enrollee did not know at the time of enrollment whether the fetus had a malformation, and (b) no prenatal testing was completed prior to enrollment.
Retrospective report	Retrospective reports of pregnancy are those in which the pregnancy ended before enrollment or at the time of first contact with the registry.

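### Section 5's precision figure (350 live births, 95% CI 1.32–5.09%) is built on the traditional prospective set, while the primary birth-defect analysis uses only the smaller pure prospective SLE subset, for which no precision is stated

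*Protocol*

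**What the plan says.** Section 5 says the registry "will seek to enroll approximately 500 traditional prospective pregnancies exposed to commercially supplied belimumab". It assumes that "approximately 83-95% of pregnancies enrolled in pregnancy exposure registries will result in a live birth" and that "approximately 20-25% will be lost to follow-up", and arrives at between 311 and 380 live births. It then gives, for belimumab-exposed participants, an "exact 95% confidence interval (CI) of (1.32%, 5.09%) assuming 350 live births" and an observed prevalence equal to the MACDP figure of 2.78%. The Protocol Summary repeats the target and the 311–380 range.

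The analysis sections use a different set. Section 4.8.2 defines the primary study population as pure prospective evaluable cases in exposed women with SLE. Section 4.8.2.2 says: "The birth defect primary analysis will include pure prospective pregnancies and a sensitivity analysis with traditional prospective pregnancies is planned". Section 4.6.8.2 keeps traditional prospective cases out of the primary population, and Section 6 repeats the split. Pure prospective is a subset of traditional prospective: the woman did not know of a malformation and had completed no prenatal testing when she enrolled. On what counts as a prenatal test, the glossary says: "Examples include ultrasound, amniocentesis, chorionic villus sampling, nuchal translucency testing, and maternal serum screening for aneuploidy or neural tube defects".

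Section 5 gives no expected pure prospective share, no pure prospective target and no interval for that subset, and no other section supplies them.

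**The concern.** The registry is descriptive, so the width of the interval is the whole justification for its size. A reader of Section 5 will take 1.32–5.09% as the precision of the primary analysis, but it was derived for the population used in the sensitivity analysis. Because the glossary lists ultrasound without exempting early scans, the primary subset could be much smaller than the enrolled total.

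It also affects when recruitment ends. Section 5 leaves recruitment open until the sample is judged adequate, and Section 7.6 refers back to Section 5 for that criterion. The only numbers there count traditional prospective pregnancies and the live births derived from them. Adequacy could therefore be judged on a count that is not the one driving the primary estimate.

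**Working it through.** **Inputs.** From Section 5: 500 pregnancies, live-birth rate 83–95%, loss to follow-up 20–25%, 350 live births, prevalence 2.78%. From Section 1.1: SLE fetal loss 15–25%. The pure prospective share is not in the protocol and is treated as an assumption. All 500 are taken to have SLE, and pure prospective women are given the same live-birth and follow-up rates as the rest.

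**Step 1: reproduce the plan's figures.** Live births = enrolled × live-birth rate × (1 − loss).
- Upper: 500 × 0.95 × 0.80 = 380.
- Lower: 500 × 0.83 × 0.75 = 311.25, i.e. 311.

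The exact (Clopper–Pearson) limits are the 2.5% quantile of Beta(x, n − x + 1) and the 97.5% quantile of Beta(x + 1, n − x). With n = 350 and x = 0.0278 × 350 = 9.73, they are 1.325% and 5.093%, which agrees with the protocol to rounding. The protocol evidently used the non-integer count, since x = 10 would give 1.38–5.19%. The same convention is used below.

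**Step 2: what 350 pure prospective live births would require.**
- Most favourable rates: 350 / (0.95 × 0.80) = 461 pure prospective pregnancies; 461 / 500 = 92% of the target.
- Least favourable rates: 350 / (0.83 × 0.75) = 562; 562 / 500 = 112%, so not attainable from 500.

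**Step 3: precision of the primary analysis by assumed pure share.** Take 350 live births in the traditional set, n = 350 × share and x = 0.0278 × n.

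| Pure share (assumed) | Live births | Exact 95% CI | Width (points) |
|---|---|---|---|
| 100% (as stated) | 350 | 1.32–5.09% | 3.77 |
| 75% | about 262 | 1.15–5.57% | 4.42 |
| 50% | 175 | 0.89–6.44% | 5.55 |
| 30% | 105 | 0.56–8.01% | 7.45 |

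**Step 4: live-birth rate, a secondary point.** Section 1.1 reports that "The proportion of pregnancies in women with SLE resulting in fetal death has been reported to be 15-20% in European studies", with 15–25% in North American studies. If 15–25% loss applied to registry enrollees, and elective terminations are ignored:
- 500 × 0.85 × 0.80 = 340 live births, CI 1.31–5.14%.
- 500 × 0.75 × 0.75 = 281 live births, CI 1.19–5.44%.

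This puts 350 above the range even before any pure prospective restriction, but the upper limit rises only from 5.09% to 5.14–5.44%. The pure share matters far more.

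**The case against.** The best defence is that Section 5 is conditional on 350 live births, the target is approximate, and recruitment is open-ended. Section 5 itself acknowledges that the number will be hard to reach, and Section 7.5 ties closure to having enough information and to consulting regulators. No test or decision threshold hangs on the interval, and the observed interval will be reported whatever number is reached. All of that stands. It does not supply a precision figure for the primary population, and it leaves the adequacy judgement without a pure prospective count to refer to.

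Several stronger readings are tempting, but the documents do not support them.
- **An arithmetic error.** There is none; 311, 380 and the interval all reproduce. The fault is the population they are attached to.
- **The precision can never be delivered.** That follows only for about 500 enrolled and depends on the pure share. Nothing caps enrollment at 500 or makes 500 a stopping rule.
- **The 83–95% is a non-SLE rate.** The protocol says only that it comes from pregnancy exposure registries. It overlaps the SLE-implied 75–85% at 83–85%. Section 4.8.4.1 notes that miscarriage prevalence depends heavily on when women enroll, so carrying cohort losses into a registry is itself an assumption.
- **The belimumab trial outcomes should size the registry.** Section 1.1 says "fetal loss was reported for 13/34 pregnancies among subjects exposed to" belimumab, but those women were on contraception and were withdrawn from treatment on a positive test. The protocol itself cautions that the numbers are very small.
- **A loss of power against MACDP.** Section 4.8.4 ties the lower-limit comparison to external SLE cohorts. The MACDP comparison in Section 4.8.4.2 is an estimated difference with an interval.
- **The definition of a prenatal test must change.** Section 5 can be corrected without touching it, and Appendix 4 records that the report definitions were adopted at the EMA's request.

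**Conclusion.** The point holds as a population mismatch. The 350-birth interval describes the traditional prospective sensitivity analysis and is optimistic for the primary analysis, which has no stated precision. That rests on the protocol's text alone. So does the 92% requirement at about 500 enrolled, given the protocol's own rates applied equally to the pure subset.

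The direction of the error is certain but its size is not. The widening from 3.77 points to between 4.42 and 7.45 depends on assumed shares of 75% down to 30%, for which the protocol offers no evidence. The SLE fetal-loss figures add a small further widening, and only if they apply to women who enroll in a registry.

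**What to change.** In Section 5:
1. Label the 350-birth interval as applying to the traditional prospective sensitivity analysis.
2. Add a short table of expected pure prospective SLE live births with the exact 95% CI for each entry, over a stated range of pure shares (updated from enrollment to date) and live-birth rates, including rates consistent with Section 1.1.
3. State that adequacy of the accumulated sample will be judged on pure prospective evaluable SLE live births, and monitor accrual on that count. Section 7.6 then picks this up through its reference to Section 5.

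Carry the same labelling into the Number of Participants entry of the Protocol Summary. The change is to text only and does not by itself require more enrollment. The downside is that the stated precision becomes less favourable.
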